NCT04626947

Title: Prevention of Recurrent Clostridium Difficile Infection (CDI) in Patients With Inflammatory Bowel Disease (IBD)

Protocol: Version 1. 10/25/2019

Study Title: Prevention of recurrent Clostridium difficile infection (CDI) in patients with inflammatory bowel disease (IBD)

Institution Name: University of Pittsburgh School of Medicine

Principal Investigator: [name], AGAF, FACG

Professor of Medicine, Clinical and Translational Science

Co-Director, UPMC Inflammatory Bowel Disease Center

Director, Translational Inflammatory Bowel Disease Research

Director, Nutrition Support Service

Division of Gastroenterology, Hepatology and Nutrition

Department of Medicine. University of Pittsburgh School of Medicine

Investigator Contact Information: [name]

[contact] [contact]

1. Objectives & Hypotheses

- a. Primary objective: Compare the short term tolerability and effectiveness of enhanced CDI therapy with Bezlotoxumab in patients with IBD after CDI. Special attention will be paid to rates of recurrent CDI, healthcare utilization, quality of life and disease activity.
- b. Secondary objective:
Evaluate the long term clinical outcomes of enhanced CDI therapy with Bezlotoxumab in patients with IBD. 90 days, 1 year and 2 year patterns of recurrent CDI, healthcare utilization, quality of life and disease activity will be assessed. We will use our published control population as well as patients who agree to be monitored but do not receive enhanced therapy as the control population.

Hypothesis: Administration of a human monoclonal antibody that binds to Clostridium difficile toxin B (Bezlotoxumab) in IBD patients with documented CDI will safely and effectively improved long-term clinical outcomes assessed by reduced rates of recurrent CDI, healthcare utilization, quality of life and disease activity and reduced overall charges associated with two year patterns of care.

2. Background & Rationale, Significance of Selected Topic & Preliminary Data

Inflammatory bowel diseases, including Crohn's disease and ulcerative colitis are lifelong chronic inflammatory conditions characterized by multiple remitting and relapsing events. During their lifetime, patients will experience multiple hospitalizations and surgical interventions as a part of the natural course of their disease. IBD patients frequently require corticosteroids, immunomodulators and biologic agents to induce and

maintain remission, which may pose a risk for infectious complications. In addition to this iatrogenic risk from immunosuppression, IBD patients have frequent contact with the healthcare environment (hospitalization, emergency department and clinic) which can further increase their risk for infection, including enteric infection with *Clostridium difficile* (*C* *difficile*)(1)(2). New evidence suggests that the gut microbiome in patients with IBD is dysbiotic, with a reduced diversity of microflora, which may predispose these patients to develop enteric infectious complications, including *C difficile* infection (CDI).(3) Epidemiologic evidence and single center studies have demonstrated that IBD patients are at increased risk of developing *C difficile* infection (CDI) and recurrent CDI, likely due to an underlying dysbiosis in their enteric flora as well as their impaired ability to mount an immune response to *C difficile* toxin, which may be linked to iatrogenic side effects of immunosuppression with systemic corticosteroids, immunomodulators and biologic agents(4).

Our group has previously demonstrated that IBD patients are at increased susceptibility for developing CDI and clinical outcomes of CDI in the IBD patient population are overall worse, with increased morbidity and mortality(5)(6). This work was performed prior to the advent of enhanced immunotherapeutics targeting *C difficile* toxins (i.e. bezlotoxumab) (7). Due to the need for uniformity in the short term clinical response to anti-*C difficile* therapy, and a clinical read out emphasizing diarrhea resolution, IBD patients were excluded from many of the pivotal trials on new agents for the treatment and prevention of CDI over the past decade. This was necessary as CDI will frequently trigger a “flare” of underlying IBD related inflammation, which will make interpretation of *C. difficile* treatment too difficult. As a result of this pragmatic trial necessity, there is very limited data regarding the effectiveness, tolerability and long-term impact of these newer agents on a high risk population of patients, who would theoretically have the most benefit from improved CDI treatment. This lack of evidence has unfortunately been used as a barrier, preventing IBD patients from gaining access to enhanced CDI treatment. Thus a “Catch-22” scenario has emerged, where IBD patients, who suffer from complex and severe CDI which frequently precipitates flare of their underlying IBD, where excluded from the pivotal trials (out of necessity), but the resulting lack of evidence now functions as a barrier to their ability to receive these more effective, albeit more costly upfront treatments.

This proposal seeks to address this knowledge gap by specifically treating IBD patients with *C difficile* antibody approaches to demonstrate effectiveness as well as improved long-term outcomes and overall cost-effectiveness.

In order to demonstrate an improved long-term natural history following enhanced *C difficile* therapy in IBD, our group had to first demonstrate the natural, multiyear history of CDI on patients with IBD using existing treatment modalities. Our recently published manuscript characterizing the long-term natural history of IBD following CDI clearly demonstrates that the underlying IBD accelerates in many of the patients experiencing this infection. This project, performed with the support of an investigator initiated study (IIS) from Merck, used a propensity score matching strategy to determine an appropriate IBD control population to assess the impact of CDI over the year of infection and the year following infection. This work led to important insights regarding CDI in IBD(5). The propensity score matching was performed in the year preceding the CDI, and the matching was carried out for 24 criteria known to be relevant for the development of CDI. IBD patients at risk for CDI were in general sicker than the average patient, with higher rates of steroid exposure, hospitalization and antibiotic exposure, compared with the

average patient in the clinic. As expected, *C difficile* exerted a negative effect on the natural history of IBD and is associated with an increase in IBD severity and healthcare utilization. During the year of CDI, IBD patients had an increased objective evidence of inflammation, increased disease activity scores and lower quality of life scores when compared to those who did not have CDI. Most importantly, we demonstrated that within this vulnerable population, CDI has a long lasting, negative effect on patient clinical trajectories, which was clearly evident in the year after infection. IBD patients with CDI continued to require antibiotics and demonstrated a 6 fold increase in healthcare charges compared with matched individuals who did not experience CDI. IBD patients with CDI generated mean healthcare charges (irrespective of pharmacy charges) of \$48,000 annually, compared with an expected median charge of \$7,000 in the matched control population.

Thus, we proposed to prospectively assess the short and long-term impact of enhanced CDI therapy in the IBD patient population with Bezlotoxumab. Having defined the natural history of CDI over a 2 year time period, we will use an identical structure to determine if there is an improvement in clinical trajectory with enhanced CDI therapy the year after infection.

3. Study Design:

This is a prospective, single center, non-randomized, observational, open label study to compare tolerability, efficacy, and short and long term clinical outcomes of Bezlotoxumab in CDI IBD patients.

A total number of 50 patients will be enrolled. Patients who agreed to receive Bezlotoxumab will be compared to our recently published historical controls as well as IBD registry patients who do not elect to receive enhanced *C difficile* therapy.

Patient population will include any patient who receives care at the Digestive Disorder Center at UPMC Presbyterian Hospital.

Inclusion criteria: >18 years old, diagnosis of IBD and CDI.

Exclusion criteria: <18 years old, no IBD, no CDI, history of colectomy.

4. Study Flowchart

Data collection:

Visit 1 (Enrollment)

- a. Demographic information
- b. type of IBD
- c. disease duration
- d. history of bowel resection
- e. current medications
- f. inflammatory markers: CRP, ESR, Albumin
- g. CBC
- h. quantitative immunoglobulins
- i. Vitamin levels (Vit D and Vit B)
- j. Disease related quality of life (SIBDQ)
- k. Disease activity scores (HBI-UCAI)
- l. Dietary intake (sugar and fat intake)

m. Stool sample

Visit 2 (90 days after enrollment)

Clinic visit or Telephone call

- a. inflammatory markers: CRP, ESR, Albumin (if available as a standard of care)
- b. CBC (if available as a standard of care)
- c. Disease related quality of life (SIBDQ)
- d. Disease activity scores (HBI-UCAI)
- e. ED visits
- f. Hospital admissions

Visit 3 (1 year after enrollment)

Clinic visit or Telephone call

- a. inflammatory markers: CRP, ESR, Albumin (if available as a standard of care)
- b. CBC (if available as a standard of care)
- c. Disease related quality of life (SIBDQ)
- d. Disease activity scores (HBI-UCAI)
- e. ED visits
- f. Hospital admissions

Visit 4 (24 months after enrollment)

Clinic visit or Telephone call

- a. inflammatory markers: CRP, ESR, Albumin (if available as a standard of care)
- b. CBC (if available as a standard of care)
- c. Disease related quality of life (SIBDQ)
- d. Disease activity scores (HBI-UCAI)
- e. ED visits
- f. Hospital admissions
- g. Total charges associated with cost of care

5. Study Procedures:

This is a prospective observational study comparing the effectiveness of Bezlotoxumab to reduce rates of CDI in patients with IBD. We will evaluate short and long-term clinical outcomes after treatment with Bezlotoxumab.

Patients who are part of the IBD Registry and have a defined IBD diagnosis and CDI will be approached to be consented for this study. Randomly the study treatment will be offered to 50 patients.

Diagnosis of CDI will be accomplished using the standard CLIA certified strategies employed in our microbiology/virology clinical laboratories, which include PCR amplification, two step GDH /gene amplification of liquid/unformed stool samples.

Patients will be divided into 2 groups of treatment and followed in a parallel fashion for the next 2 years: 1. Those who agree to receive Bezlotoxumab (Case) and 2. Those who do not agree to received Bezlotoxumab (controls).

6. Study Duration:

Total duration time: 5 years. 36 months enrollment and 24 months follow up.

7. Statistical Analysis and Sample Size Justification:

Sample size: 50 (Based on the prevalence of CDI within our patient population)

Descriptive statistics of baseline characteristics will be used to characterize the 50 IBD CDI patients who agree to receive Bezlotoxumab. The baseline characteristics under consideration include demographic data, type of IBD, duration of IBD, current medications, inflammatory markers, SIBDQ, HBI-UCAI and others collected at the time of enrollment. Mean, standard deviation, median and interquartile range will be reported on continuous variables and proportions reported on discrete variables.

Similar baseline characteristics will be collected at enrollment among historical controls and IBD registry patients who do not elect/ not offered to receive enhanced C difficile therapy. Similar descriptive statistics will be used to characterize these controls. A logistic regression model will be developed to predict the status of receiving Bezlotoxumab from the extensive list of baseline characteristics. Subsequently each study participant, including both the 50 patients who receive Bezlotoxumab and the controls, will be assigned a predicted probability of treatment based on this propensity score model. The inverse probability weighting method will be used to compare the Bezlotoxumab-treated IBD CDI patients and the controls in baseline characteristics to demonstrate balanced baseline characteristics between the two groups after inverse probability weighting (8).

In the primary analysis, we will compare the risk of recurrent CDI between the 50 treated and 118 controls at 90 days after enrollment. The inverse propensity score-weighted method will be used to estimate the proportion of recurrence CDI at 90 days under Bezlotoxumab among IBD CDI patients seen in the clinics and compared with that for IBD CDI patients without Bezlotoxumab. Other long-term outcomes for comparison include, number of healthcare utilization (emergency room visits and hospitalization), overall charges during the second year after the study enrollment; inflammatory markers and CBC (in continuum and binary: abnormal vs normal), SIBDQ, HBI-UCAI, dietary intake at the 90 days, 12-month and 24-month visits. The inverse probability-weighted method will be used to compare these outcomes between Bezlotoxumab-treated and controls with IBD CDI. Cardiac failure will be closely monitored throughout this study and the proportions of cardiac failure among the 50-treated patients by the first 90 days, 12 months and 24 months will be estimated. The paired t-test or the nonparametric signed-rank test will be used to test the change baseline to the 24-month visit in continuous outcomes and the McNemar test will be used to for discrete outcomes.(9)

Using data from the 50 IBD CDI patients, linear-mixed models and generalized linear-mixed models will be used to explore the longitudinal change in the repeatedly measured assessments of disease activity and quality of life, including current medications, inflammatory markers, annual overall financial charges, annual use of healthcare facilities (such as emergency room visit and number of hospitalizations) SIBDQ, and HBI-UCAI. Trajectory analyses on these multiple longitudinal patient outcomes will be used to identify IBD CDI patients who have responded to the treatment and who have not. Subsequently we will compare the baseline patient characteristics between the treatment responders and non-responders and the results will be invaluable in guiding future management of IBD CDI patients.

Based on data from 28 IBD CDI patients, it was reported that the proportion of IBD patients with recurrent CDI within 12 weeks of follow-up was 26.7% among Bezlotoxumab-treated and 53.8% among those without Bezlotoxumab (10-11). With 118 controls and 50 Bezlotoxumab-treated patients, we will have 88% power to detect the same difference by using the Fisher's Exact test with a 2-sided alpha level at 0.05.

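### Follow-up laboratory outcomes exist only when drawn for routine care, and neither the complete-pair change tests nor the treatment-only weights allow for who was tested

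*Combined protocol and SAP*

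**What the plan says.** **Collection (Section 4, Study Flowchart).** At enrollment the laboratory items carry no condition: "f. inflammatory markers: CRP, ESR, Albumin", with CBC listed next. At Visits 2, 3 and 4 the entries become "inflammatory markers: CRP, ESR, Albumin (if available as a standard of care" and "CBC (if available as a standard of care". Each of these visits is a "Clinic visit or Telephone call". SIBDQ, HBI-UCAI, ED visits and admissions are listed at the same visits without the condition.

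**Use (Section 7).**
- Between groups, the outcomes include "inflammatory markers and CBC (in continuum and binary: abnormal vs normal), SIBDQ, HBI-UCAI, dietary intake at the 90 days, 12-month and 24-month visits". The method is stated as follows: "The inverse probability-weighted method will be used to compare these outcomes between Bezlotoxumab-treated and controls with IBD CDI".
- For change, "The paired t-test or the nonparametric signed-rank test will be used to test the change baseline to the 24-month visit" in continuous outcomes, with McNemar's test for discrete ones. Laboratory values are not excluded.
- For the 50 treated patients, linear and generalized linear mixed models are planned for a list that names inflammatory markers but not CBC. Trajectory analyses of these outcomes then separate responders from non-responders.

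**Weights (Section 7).** The propensity model predicts receipt of bezlotoxumab from baseline characteristics. The document gives no missing-data method, no time window for routine laboratory values, no expected availability and no sensitivity analysis.

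**The concern.** A value that exists only because a clinician ordered the test is not a random sample of the group. Section 2 reports that CDI in IBD goes with greater severity and greater healthcare use, so it is plausible that patients who are unwell are tested more often than those who are well and followed up by telephone. Section 7 has no step that deals with this. Treatment weights balance the groups on who received the drug, not on who later had blood drawn. Paired tests drop every patient without a 24-month value.

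At stake are the laboratory comparisons at three time points, the laboratory change tests, and to a lesser degree the responder classification, which the plan intends to use to guide later patient care.

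**Working it through.** **1. The plan's own figure.** The only numerical claim near this point is 88% power for 90-day recurrence (53.8% of 118 controls against 26.7% of 50 treated, Fisher's exact test, two-sided 0.05). The normal approximation with continuity correction uses:
- pooled rate = (118×0.538 + 50×0.267)/168 = 0.457
- SE under the null = √[0.457×0.543×(1/118 + 1/50)] = 0.0841
- SE under the alternative = √[0.538×0.462/118 + 0.267×0.733/50] = 0.0776
- correction = 0.5×(1/118 + 1/50) = 0.0142
- power = Φ[(0.271 − 0.0142 − 1.96×0.0841)/0.0776] = Φ(1.19) = 88.2%

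This matches the stated 88%. Full enumeration of Fisher's test gives 90.0%. No laboratory value enters the calculation. The plan states no figure for the laboratory outcomes, so every draw rate below is an assumption.

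**2. Binary outcome (abnormal or normal).** Let q be the true abnormal rate, and a and b the probabilities of a draw if abnormal or normal. Then

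observed abnormal rate = q·a / [q·a + (1 − q)·b].

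Take q = 0.30 in both groups, so there is no true effect, and a = 0.90 in both. For treated patients b = 0.80, giving 0.27/(0.27 + 0.56) = 32.5%. For controls, vary b:

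| Control b | Observed in controls | Spurious gap (points) |
|---|---|---|
| 0.80 | 0.27/0.83 = 32.5% | 0 |
| 0.70 | 0.27/0.76 = 35.5% | 3 |
| 0.60 | 0.27/0.69 = 39.1% | 7 |
| 0.50 | 0.27/0.62 = 43.5% | 11 |
| 0.40 | 0.27/0.55 = 49.1% | 17 |

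The gap favours treatment here. Exchanging the two groups' draw rates reverses its sign. If both groups are drawn at 90% and 50%, each shows 0.27/0.62 = 43.5% instead of 30%, and there is no spurious gap.

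**3. Continuous outcome.** This was simulated with a standard normal value (higher = worse) and a logistic draw probability with a given odds ratio (OR) per SD of that value.
- *Single-group mean at follow-up.* OR 1 gives no bias. With ORs from 1.5 to 3, the mean is too high by 0.16 to 0.35 SD at 60% coverage. Over coverage from 80% to 40% the range is 0.08 to 0.53 SD. If healthier patients were drawn more often (OR 0.67), the bias is −0.08 to −0.23 SD.
- *Between groups, no true effect, same draw mechanism.* No bias.
- *Between groups, true effect −0.5 SD, same mechanism, 60% control coverage.* The observed effect is −0.48 (OR 1.5), −0.45 (OR 2) or −0.41 (OR 3).
- *Between groups, no true effect, 80% treated and 50% control coverage.* Spurious differences of −0.12, −0.18 and −0.25 SD appear for ORs of 1.5, 2 and 3.

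**4. Paired t-test in the treated group.** Inputs: 50 patients, 60% with a 24-month value (about 30 pairs), correlation 0.5, no true change. Type I error is 4.9% (OR 1), 6.9% (OR 1.5), 10.5% (OR 2) and 16.3% (OR 3).

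**The case against.** Several points on the other side stand.

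- **Who is tested is inferred.** No section says which patients have routine blood tests or how often. Section 2 links CDI with severity and healthcare use, not with laboratory availability. A reader might infer that sicker patients are over-represented and that the results are biased. The documents support only exposure to such bias, with no safeguard.
- **Different follow-up by group is not established.** Section 5 says that treated patients and decliners are followed in parallel for two years, and Section 4 gives one visit schedule. A gap in drawing is more plausible for the published historical controls (Section 3), but the document does not describe how their values were obtained.
- **Part of the remedy is already planned.** The mixed models in Section 7 can use all available visits, and they are less exposed if availability depends on observed data in the model. They cover only the treated patients, so they protect neither the weighted group comparison nor the paired tests.
- **The trajectory problem is narrower than the full laboratory list.** Inflammatory markers are named there; CBC is not.
- **An availability model has limits.** Follow-up SIBDQ, HBI-UCAI and healthcare-use data are not shown to exist for historical controls. With 50 treated patients, a product of two estimated weights may be unstable. The approach also corrects only for selection that the modelled variables explain.

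None of this supplies a method for values missing because no test was ordered.

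**Conclusion.** The concern holds as a conditional one. If drawing depends on illness, within-group laboratory change is likely to be biased. The between-group comparison is biased as well if drawing differs by group or if there is a true effect. With the same draw mechanism and no true effect, the group difference is unbiased.

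The size is not known from the documents. The binary scenarios give 0 to 17 points, in either direction. A reader might take 17 points as an estimate, but it is the end of an assumed range and requires normal values to be drawn half as often in controls as in treated patients. The paired-test error of 6.9% to 16.3% likewise rests on assumed 60% coverage and ORs of 1.5 to 3.

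A reader might also infer that the trial's main result is compromised. It is not: 90-day recurrence and its 88% power use no laboratory value. Nor does the condition attach to SIBDQ, HBI-UCAI, ED visits or admissions. The plan should be changed on this point, but the matter is confined to the laboratory outcomes and the analyses that use them.

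**What to change.** Add no blood draws. Amend Section 7 as follows.

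1. **Change from baseline.** For laboratory outcomes, make the mixed models already planned for the 50 treated patients the main analysis, using all visits, in place of paired t, signed-rank and McNemar tests on complete pairs.
2. **Group comparison.** Multiply the treatment weight by a stabilised, truncated inverse probability that the laboratory value was available at that visit. Model this from baseline variables, group, SIBDQ, HBI-UCAI, ED visits and admissions. Where these data do not exist for controls, for example historical controls, label the laboratory comparison exploratory.
3. **Reporting and sensitivity.** Tabulate laboratory availability by group and visit. Add a sensitivity analysis in which availability depends on the unobserved value, since neither step 1 nor step 2 covers that case.
4. **Responder trajectories.** Run them without routine-care laboratory values, at least as a sensitivity analysis.

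The cost is SAP wording, one more model and wider intervals for these secondary outcomes, with possible weight instability given 50 treated patients. The sponsor would also need to check which follow-up variables the controls have.

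### The propensity model's baseline data include no prior CDI episodes, no CDI severity grade and no prior-year hospital, steroid or antibiotic history, so residual confounding of the 90-day recurrence comparison cannot be excluded

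*Combined protocol and SAP*

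**What the plan says.** The primary analysis is stated in Section 7: "we will compare the risk of recurrent CDI between the 50 treated and 118 controls at 90 days after enrollment". The groups are to be made comparable by inverse propensity weighting. The propensity score comes from a logistic regression of treatment on the baseline characteristics.

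Section 7 describes those characteristics as follows: "The baseline characteristics under consideration include demographic data, type of IBD, duration of IBD, current medications, inflammatory markers, SIBDQ, HBI-UCAI". The same sentence then adds further items, but only items collected at enrollment. The model has no covariate list of its own.

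Section 4 itemises Visit 1 from a to m: demographics, IBD type, disease duration, "history of bowel resection", current medications, CRP/ESR/albumin, CBC, immunoglobulins, vitamin levels, SIBDQ, HBI-UCAI, diet and a stool sample. ED visits and hospital admissions first appear at Visit 2, as follow-up data.

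Section 2 describes the group's earlier propensity-matched study, which used data from the year before infection: "the matching was carried out for 24 criteria known to be relevant for the development of CDI". It reports that IBD patients at risk for CDI were sicker than the average clinic patient, "with higher rates of steroid exposure, hospitalization and antibiotic exposure".

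**The concern.** Weighting can balance only what has been measured. It is the only control of confounding planned for the primary endpoint, and its inputs mostly describe the bowel disease. The endpoint is return of the infection, yet nothing in the inputs records the infection's own history.

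Three features of the design give these factors room to differ between groups:

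- Eligibility (Section 3) requires IBD and CDI. It does not separate first from repeat episodes or set a severity level.
- Section 5 offers the drug at random, but then forms the groups by who agrees and who does not.
- Historical controls are added. They come from work done before the drug was available (Section 2), so they had no offer to accept or decline.

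At stake is how the 90-day recurrence difference can be read. If an unmeasured predictor of recurrence is less common among treated patients, part of the difference will be wrongly credited to the drug. If it is more common among them, a real benefit will be diluted.

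**Working it through.** **1. The two lists side by side**

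| Item | Visit 1 (Section 4) | Section 7 covariates |
|---|---|---|
| Number of prior CDI episodes | Not listed | Not listed |
| CDI severity grade | Not listed; CBC, albumin and CRP are partial proxies | Inflammatory markers named; CBC can enter as an enrollment item |
| Anti-CDI drug for index episode | Possibly within current medications, not itemised | Same |
| Admissions and ED visits, prior 12 months | Not listed | Not listed |
| Steroids and antibiotics, prior 12 months | Current use only, at most | Same |

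Because the open-ended part of the Section 7 sentence is tied to enrollment data, it cannot bring in an item that Visit 1 does not collect.

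**2. The plan's own power figure**

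Inputs from Section 7: recurrence of "26.7% among Bezlotoxumab-treated and 53.8% among those without Bezlotoxumab", a difference of 53.8 − 26.7 = 27.1 points. The group sizes are 50 treated and 118 controls, the test is Fisher's at a two-sided 5% level, and the stated power is 88%.

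Exact enumeration over both binomial distributions gives 88.4% when the two-sided p-value is the doubled one-sided value. The continuity-corrected normal approximation gives 88.2%. The stated 88% is reproduced and is not in dispute. With the minimum-likelihood definition of the two-sided p-value, used below, power is 90.0%. With both true risks at 53.8%, the rejection rate is 4.1%.

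**3. Size of a possible bias (assumed inputs)**

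The documents give neither the prevalence nor the strength of any of these factors. Assume recurrence of 25–35% after a first episode and 50–60% with prior episodes, and prior episodes in 50–60% of one group and 25–30% of the other.

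Bias = (difference in prevalence) × (difference in recurrence risk)

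- Smallest: (50% − 30%) × (50% − 35%) = 0.20 × 0.15 = 3.0 points
- Largest: (60% − 25%) × (60% − 25%) = 0.35 × 0.35 = 12.25 points

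**4. Effect on an unweighted Fisher test, 50 versus 118, control risk 53.8%**

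| Bias | False-positive rate if it favours the drug (treated risk 53.8% − bias) | Power if it hides benefit (treated risk 26.7% + bias) |
|---|---|---|
| 0 | 4.1% | 90.0% |
| 3.0 points | 5.5% | 81.2% |
| 7.5 points | 12.7% | 62.2% |
| 12.25 points | 27.9% | 39.3% |

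One limit of this table is that the assumed strata imply a control risk of at most 0.60 × 60% + 0.40 × 35% = 50%, slightly below the 53.8% used.

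**5. Cross-check with control risk held at 53.8%**

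Take one unmeasured binary factor with a recurrence risk ratio RR and no drug effect. Risk without the factor is p0 = 0.538 / (1 − pc + pc × RR), where pc is its prevalence in controls. Apparent treated risk is p0 × (1 − pt + pt × RR), where pt is its prevalence in treated patients.

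- pt 30%, pc 50%, RR 1.5: p0 = 0.538/1.25 = 0.430; treated risk 0.430 × 1.15 = 0.495; bias −4.3 points; rejection rate 6.9%.
- pt 20%, pc 50%, RR 2.0: p0 = 0.538/1.5 = 0.359; treated risk 0.359 × 1.2 = 0.430; bias −10.8 points; rejection rate 22.3%.
- Reverse imbalance (pt 50%, pc 20%) with the planned drug effect: power 78.8% at RR 1.5 and 66.1% at RR 2.0.

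**6. Could one such factor explain the whole planned effect?**

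The planned ratio is 0.538/0.267 = 2.015. The E-value is 2.015 + √(2.015 × 1.015) = 3.4. A factor would need associations of about 3.4 with both treatment and recurrence.

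**The case against.** Several counter-arguments have weight.

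- **Index treatment may already be captured.** Patients enroll with CDI, so current medications can include the anti-CDI drug, current antibiotics and current steroids. This stands: index treatment is unspecified, not clearly omitted. What is missing is itemisation, a look-back, and a definition for historical controls.
- **Severity is partly covered.** CBC, albumin and CRP are collected. This also stands, but they say nothing about earlier episodes or prior-year exposure.
- **The offer is random, and Section 7 allows controls who were not offered the drug.** This narrows the part that patient choice plays. It does not remove it, because acceptance still defines the treated group, and historical controls add differences of era.
- **Section 2 concerns another question.** The 24 criteria relate to developing CDI and served to match infected with uninfected patients. No passage ranks predictors of recurrence. This stands, so the earlier study shows only that prior-year data of this kind were considered relevant and were usable.

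A reader might go further and infer that the weighted comparison will certainly be confounded, or that patients with repeated CDI will accept the drug more often and so make it look effective. The documents support neither. They do not say who accepts, and that pattern would place higher-risk patients in the treated group and hide benefit. Only the opposite imbalance raises the false-positive rate.

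**Conclusion.** The gap is real and can be seen in the text, and the direction and size of its effect are unknown. The plan as written cannot adjust for CDI history, a CDI severity grade or prior-year exposure, and it does not say that the earlier study's criteria are carried into Section 7.

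The ranges in the working rest entirely on assumed prevalences and risks and describe an unweighted test. They ignore partial adjustment through correlated covariates. They show that a plausible imbalance could matter, not that one exists. Even the largest assumed bias, 12.25 points, is under half of the planned 27.1, so one factor of this kind is unlikely to account for the whole assumed effect. This is a worthwhile, inexpensive improvement to the primary analysis and does not invalidate the design.

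**What to change.** Add these fields to Visit 1 and name them in the Section 7 propensity model:

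- number of prior CDI episodes;
- severity of the index CDI episode, by a stated definition;
- anti-CDI drug given for the index episode, itemised from current medications;
- hospitalizations, ED visits, systemic steroids and antibiotics in the prior 12 months.

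Abstract them from the registry or health record by the same rules for treated, concurrent and historical patients. Where a field cannot be retrieved for historical controls, say so. Prespecify a sensitivity analysis for unmeasured confounding, such as an E-value or a bias analysis over stated ranges.

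The cost is some chart abstraction, with no new visit or procedure. The earlier study used pre-infection-year data, but nothing in the documents shows that episode counts or severity can be recovered for historical controls, so missing values are likely to need handling. The model also grows while the treated group stays at 50, so lower-value covariates such as vitamin levels may have to be dropped.
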